- (9) Must only be taken if Visit 9 is later than 1 month after Visit 8, otherwise blood sample from Visit 8 will be used as pre-booster sample.
- (10) Samples have to be obtained before vaccination. Urinalysis and pregnancy results must be available before vaccination.
- (11) In women of childbearing potential. A woman is considered of childbearing potential if fertile, following menarche and until becoming post-menopausal unless permanently sterile. A woman that is considered of non-childbearing potential must be e.g. surgically sterilized for at least 3 months prior to Visit 9 (e.g. by hysterectomy, bilateral salpingectomy, bilateral oophorectomy, transcervical sterilization), or postmenopausal for at least one year prior to Visit 9.
- (12) Creatinine, sodium, potassium, calcium, aspartate aminotransferase (AST), alanine aminotransferase (ALT), alkaline phosphatase, bilirubin, CRP (blood: 8.5 mL). Tests that were performed in study laboratory within visit window and where results are available at study visit are acceptable.
- (13) Hemoglobin, hematocrit, erythrocyte count, white blood count, platelets (Ethylenediaminetetraacetic acid [EDTA] blood: 4 mL). Tests that were performed in study laboratory within visit window and where results are available at study visit are acceptable.
- (14) Standard urine dipstick: pH, specific gravity, leucocytes, nitrite, protein, glucose, ketones, urobilinogen, bilirubin, erythrocytes. Tests that were performed in study laboratory within visit window and where results are available at study visit are acceptable.
- (15) Blood is collected for immunogenicity testing by ELISA and for supportive functional antibody analysis by serum bactericidal assay or animal protection models.
- (16) To be performed by study staff otherwise not involved with study conduct to keep the study observer-blinded (i.e. un-blinded study staff).
- (17) Vaccination has to be administered by study staff otherwise not involved with study conduct to keep the study observer-blinded. Subjects enrolled in the Booster Phase should be observed for at least 30 min after vaccination for treatment of any immediate reactions.
- (18) Body systems for which the subject reports any symptoms should be evaluated and relevant abnormal findings documented as AEs. At vaccination day the symptom-driven physical exam is to be performed before administration of the vaccination

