4. INVESTIGATIONAL PLAN

4.1 Study Endpoints

Primary Endpoint:

- + GMTs (Geometric Mean Titers) for IgG against each OspA serotype ST1 to ST6, determined by ELISA at Day 208 (Month 7).

Secondary Endpoints:

Immunogenicity:

Main Study Phase:

- + GMTs for IgG against each OspA serotype (ST1 to ST6), determined by ELISA, at Day 1 (Month 0), 29 (Month 1), 57 (Month 2), 85 (Month 3), 180 (Month 6), 365 (Month 12), and 545 (Month 18).
- + SCRs (Seroconversion Rate, defined as rate of subjects that change from seronegative[†] at Visit 1 (baseline) to seropositive[†], if seronegative at baseline, or that achieve a four-fold increase in IgG titer compared to baseline, if seropositive at Visit 1 for each OspA serotype specific IgG (ST1 to ST6), determined by ELISA, at Day 29 (Month 1), 57 (Month 2), 85 (Month 3), 180 (Month 6), 208 (Month 7), 365 (Month 12), and 545 (Month 18).
- + GMFR (Geometric Mean of the fold rise) as compared to baseline for IgG against each OspA serotype (ST1 to ST6), determined by ELISA, at Day 29 (Month 1), 57 (Month 2), 85 (Month 3), 180 (Month 6), 208 (Month 7), 365 (Month 12), and 545 (Month 18).
- + GMTs, SCRs and GMFRs for IgG against each OspA serotype (ST1 to ST6), determined by ELISA, at Day 1 (Month 0), 29 (Month 1), 57 (Month 2), 85 (Month 3), 180 (Month 6), 208 (Month 7), 365 (Month 12), and 545 (Month 18) stratified by age group.

Booster Phase (applicable for a subset of subjects participating in booster phase):

- + GMTs for IgG against each OspA serotype (ST1 to ST6), determined by ELISA, at Day 1 (Month 0), 29 (Month 1), 57 (Month 2), 85 (Month 3), 180 (Month 6), 365 (Month 12), 545 (Month 18), Month 19, Month 24 and Month 30.
- + SCRs for each OspA serotype specific IgG (ST1 to ST6), determined by ELISA, at Day 29 (Month 1), 57 (Month 2), 85 (Month 3), 180 (Month 6), 208 (Month 7), 365 (Month 12), 545 (Month 18), Month 19, Month 24 and Month 30.
- + GMFR as compared to baseline for IgG against each OspA serotype (ST1 to ST6), determined by ELISA, at Day 29 (Month 1), 57 (Month 2), 85 (Month 3), 180 (Month 6), 208 (Month 7), 365 (Month 12), 545 (Month 18), Month 19, Month 24 and Month 30.
- + GMFR as compared to Day 208 for IgG against each OspA serotype (ST1 to ST6), determined by ELISA at Month 19, Month 24 and Month 30;
- + GMFR as compared to Month 18 (pre-boost) for IgG against each OspA serotype (ST1 to ST6), determined by ELISA at Month 19, Month 24 and Month 30;

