4.2.6 Study duration

Study duration per subject in the Main Study Phase is approximately 20 months:

- Screening period: max. 21 days
- Treatment period: 6 months (+/- 7 days)
- Follow-up period: 12 months (+/- 28 days) after the third vaccination

Overall study duration of the Main Study Phase is estimated to be 22 months.

Study duration per subject in the Booster Phase is a maximum of approximately 13 months.

Study duration per subject in the Main Study Phase and Booster Phase together is estimated to be a maximum of approximately 33 months.

Overall study duration (i.e., First-Subject-In to Last-Subject Out/ end of Booster Phase) is estimated to be approximately 37 months.

The end of the study is defined as the date of the last visit performed by the last subject.

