4.2.9 Randomization

Subjects were to be allocated to treatment groups via the EDC system. Eligible subjects were to be randomized 2:2:1 stratified by study site, age group and baseline *B.b.* s.I. serostatus according to a randomization list created by a statistician. Date and time of enrollment were to be defined as the time point at which the subject is registered in the system and the subject is allocated to a treatment group.

^{*} From the 18th birthday until the last day before the 66th birthday

[†] From the 18th birthday until the last day before the 50th birthday

[‡] From the 50th birthday until the last day before the 66th birthday

All eligible subjects enrolled in the Booster Phase will be randomized 2:1 to receive an additional VLA15 180 µg vaccination or Placebo according to a randomization list created by a statistician.

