The blind must not be broken for anyone involved in the trial conduct. Unblinding of individual cases can be performed by the investigator in case of emergency and if knowledge of the treatment assignment is mandatory for emergency treatment. Designated personnel at the CCI /Pfizer safety and a sponsor representative otherwise not involved in the study conduct may be unblinded for individual cases of SAEs that are both unexpected and suspected to have a causal relationship to the trial vaccines (SUSARs), to fulfil safety reporting requirements. Procedures are described in a safety management plan. The same blinding/emergency unblinding procedures as in the Main Study Phase will be applied during the Booster Phase.

The study sponsor/collaboration partner and trial statisticians will be unblinded at the time of the Day 208 Interim Analysis (primary endpoint analysis), after the respective database

snapshot has been performed. All other study personnel including investigators and other study staff involved in general study conduct and safety assessments as well as laboratory personnel who are performing analytical assays remain blinded and will remain blinded until start of Month 18 visits (Visit 8). As only subjects randomized in the 180 µg dose group during the Main Study Phase will be included in the Booster Phase, partial unblinding of the study site staff and subjects will occur, as subjects that will be asked to continue the study will know that they had been randomized to the VLA15 180 µg group in the Main Study Phase. Investigators will be informed shortly prior to the start of Visit 8 which subjects they should ask to continue in the study via a list of subjects that will be provided by Data Management. Investigators and other site staff will therefore be partially unblinded shortly prior to Visit 8. Subjects who are not being invited will not be able to ascertain if they have been enrolled to the VLA15 135 µg group or the placebo group. Booster subjects, sponsor and investigator/site staff involved in clinical evaluation of subjects will however be blinded for the Booster Phase, i.e., they will not know if subjects that continue the study in the Booster Phase will receive VLA15 180 µg or Placebo.

In the Booster Phase the study sponsor/collaboration partner and trial statisticians will be unblinded at the time of the Month 19 analysis, after the respective database snapshot has been performed.

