All immunogenicity analyses will be performed for the PP population. It will be described in the SAP which analyses will be repeated for the mITT population and which analyses will also be repeated stratified by baseline *B.b. s.l.* serostatus and by age. Study sites with low enrollment numbers per randomization stratum will be combined in these analyses, further details will be provided in the SAP.

Booster Phase:

The primary immunogenicity analysis will provide 95 % Confidence Intervals for Geometric Mean Titers (GMTs) of serotype specific IgG against each OspA ST1 to ST6 as determined by ELISA in the Booster PP population at Visit 10 (Month 19). GMTs and GMT ratios will be estimated by applying an analysis of variance (ANOVA) including the factor treatment group and study site. This will be done using log10 transformed data and taking the anti-log of the resulting point estimates for the least squares means, least squares means differences and the corresponding 95 % CIs. In addition, sensitivity analyses (ANOVAs with factors study site, treatment group, study site*treatment group, age, and *B.b. s.l* serostatus at baseline) will be performed.

As secondary analysis, GMTs and 95%CI will be provided at Month 18 (Visit 9), Month 24 (Visit 11), and Month 30 (Visit 12). Analyses will compare the VLA15 group against the placebo group.

Further secondary immunogenicity analyses will provide the following:

- The Geometric Mean of the fold rise (GMFR) at Visit 10 (Month 19) as compared to Visit 1 (baseline), Visit 6 (Day 208, peak titer after primary immunization series) and Visit 9 (pre-boost) for IgG against each OspA ST 1-6 as determined by ELISA (ANOVA) and SBA, if applicable.
- Seroconversion Rates against each OspA serotype separately at all study visits (ELISA and SBA).
- GMTs for IgG against each OspA serotype (ST1 to ST6), determined by ELISA, at specified time points, by age group.

* An ELISA titer below 40 U/mL (i.e., the quantitation limit of the ELISA) is considered "OspA IgG seronegative". Values will be replaced by 20 U/mL.

† An ELISA ≥40 U/mL is considered "OspA IgG seropositive".

All immunogenicity analyses of the Booster Phase will be performed for the Booster PP Population. It will be described in the SAP whether any analyses will be repeated for the Booster mITT.

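### The booster GMT comparisons never adjust for the pre-booster titer the trial collects, which costs precision; as a minor point, the main-phase primary model omits two of its three randomisation strata

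*Protocol*

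**What the plan says.** **Booster model.** Section 9.3 (Booster Phase) says "GMTs and GMT ratios will be estimated by applying an analysis of variance (ANOVA) including the factor treatment group and study site", on log10 data. The Statistical Methods part of the synopsis names the same two factors for the comparisons at Months 18, 19, 24 and 30. The additional models are "sensitivity analyses (ANOVAs with factors study site, treatment group, study site*treatment group, age, and" baseline *B.b. s.l.* serostatus. None includes an OspA titer.

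**Pre-booster titer.** A sample is taken at Visit 9 if that visit falls more than one month after Visit 8; "otherwise blood sample from Visit 8 will be used as pre-booster sample" (Table 4, footnote 9). Its only use as a baseline is the fold rise: section 4.1 lists "GMFR as compared to Month 18 (pre-boost) for IgG against each OspA serotype (ST1 to ST6") at Months 19, 24 and 30, and the synopsis agrees. Section 9.3 names Visit 10 only, in the item that begins "The Geometric Mean of the fold rise (GMFR) at Visit 10 (Month 19) as compared to Visit 1 (baseline").

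**Booster randomisation.** Section 4.2.9: "All eligible subjects enrolled in the Booster Phase will be randomized 2:1 to receive an additional VLA15" 180 µg vaccination or placebo. No stratification factor is named. Section 9.6 expects at most 81 participants and makes no formal sample size calculation for this phase.

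**Main phase.** Randomisation is stratified by site, age group and baseline serostatus (section 4.2.9). The primary ANOVA in section 9.3 has treatment and site only. Age and serostatus enter only a sensitivity model that also carries the site-by-treatment interaction.

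**The concern.** A subject's titer just before the booster is likely to predict the titer afterwards, above all in the placebo arm. Leaving it out has two costs.

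- **Precision.** The variation that the pre-booster titer explains stays in the residual, so the interval for the GMT ratio is wider than it need be.
- **Chance imbalance.** With about 54 versus 27 subjects and no stratification stated, the arms may differ before the injection. That difference carries into the GMT ratio multiplied by the pre/post correlation. It carries into the fold-rise ratio in the opposite direction, multiplied by one minus the correlation. The two planned estimates therefore differ by exactly the pre-booster imbalance, and no planned model reconciles them.

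Whether the booster produces a response at Month 19 probably does not depend on this: section 1.4.3.1 reports Phase 1 booster GMTs at 2.7 to 5.8 times the primary-series peak. What is at stake is the size of the ratio and the persistence comparison at Months 24 and 30. Section 1.5 gives persistence with and without a booster as a reason for this phase.

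**Working it through.** **The plan's own figure.** Section 9.6 claims 80% power with 90 evaluable per group, log10 SD 0.51, two-sided 5%, and GMTs of 61.3 and 100.4. The ratio is 100.4/61.3 = 1.638, a log10 difference of 0.2143. The noncentral t gives 80.0%, so the figure reproduces. The booster phase has no stated figure to reproduce.

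**Booster inputs.** 81 subjects at 2:1 gives 54 and 27. Assumed: SD 0.51 carries over from Phase 1 (90 µg, ST1) and is equal before and after the booster. The within-arm pre/post correlation ρ is not in the protocol, so a range is shown.

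**Formulas for the SE of the log10 ratio.**
- Planned ANOVA: 0.51 × √(1/54 + 1/27) = 0.1202
- ANCOVA on pre-booster log10 titer: 0.1202 × √(1 − ρ²) × √(1 + 1/77)
- Fold rise from Month 18: 0.1202 × √(2(1 − ρ))

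| ρ | ANOVA | Fold rise | ANCOVA | ANCOVA vs ANOVA | ANCOVA vs fold rise |
|---|---|---|---|---|---|
| 0.3 | 0.120 | 0.142 | 0.115 | 4% smaller | 19% smaller |
| 0.5 | 0.120 | 0.120 | 0.105 | 13% smaller | 13% smaller |
| 0.7 | 0.120 | 0.093 | 0.086 | 28% smaller | 7% smaller |
| 0.9 | 0.120 | 0.054 | 0.053 | 56% smaller | 2% smaller |

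**Interval width.** The 95% limits are the GMT ratio multiplied and divided by 10^(1.96 × SE). That factor is 1.72 for the ANOVA, and 1.60 (ρ = 0.5) or 1.48 (ρ = 0.7) for the ANCOVA. Ignoring the small-sample term, a plain ANOVA would need 81/(1 − ρ²) subjects to match: 108 at ρ = 0.5 and 159 at ρ = 0.7.

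**Unequal correlations.** A simulation of 6,000 trials with five sites, ρ = 0.5 in boosted subjects and 0.9 in placebo, gave SEs of 0.121 (ANOVA), 0.085 (fold rise) and 0.082 (ANCOVA).

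**Imbalance.** A pre-booster imbalance of one SE is 10^0.1202 = 1.32-fold. It shifts the unadjusted GMT ratio by 10^(ρ × 0.1202): 1.15-fold at ρ = 0.5 and 1.21-fold at ρ = 0.7. The log fold rise is the log post titer minus the log pre titer, so in the same subjects the GMT and fold-rise ratios then differ by the full 1.32-fold.

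**Missing pre-booster samples.** Dropping a share m of subjects inflates the variance by about 1/(1 − m), so the gain over ANOVA is lost only when m exceeds about ρ²: 9%, 25% or 49% at ρ = 0.3, 0.5 or 0.7.

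**Main phase.** The protocol gives no stratum effects, so titer ratios are assumed.
- Age group (2:1 enrolment, p(1 − p) = 2/9), ratio 1.3 to 2: R² = log10(ratio)² × (2/9)/0.51² = 1.1% to 7.7%.
- Serostatus (about 10% seropositive, p(1 − p) = 0.09), ratio 1.5 to 3: R² = 1.1% to 7.9%.
- Together about 2% to 16%. The SE falls by 1% (√0.98 = 0.99) to 8% (√0.84 = 0.92), and power at the planned 1.64-fold difference rises from 80.0% to between 80.8% and 86.4%.

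**Timing.** Section 4.2.6: "Overall study duration of the Main Study Phase is estimated to be 22 months". July 2019 plus 22 months is May 2021. Adding up to 2 months to Visit 9 and 28 days to Visit 10 gives about August 2021, before version 6.0 (02-Nov-2021). Month 24 visits (Visit 9 plus 6 months) would end about January 2022. The whole study (37 months) would end about August 2022.

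**The case against.** The planned ANOVA is unbiased, and the main-phase omission is if anything conservative. The booster phase has no power claim or success criterion that adjustment could alter. The fold rise from Month 18 already uses the pre-booster titer, so against the better of the two planned analyses the ANCOVA's SE gain is only 4%, 13%, 7% and 2% at ρ = 0.3, 0.5, 0.7 and 0.9. Month 18 GMTs are compared between the booster arms, so an imbalance would be seen. The correlation is unknown, the Month 19 data may already be unblinded, and an SAP that is not shown could add a covariate model.

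Most of this stands as a limit on size: the loss is one of precision, and it may be small. It does not remove the point. The better planned analysis depends on an unknown correlation, whereas the ANCOVA has the smallest SE at every value shown. The fold rise is also a separate endpoint; at ρ = 0.3 it is less precise than the plain ANOVA, and section 9.3 does not list it after Month 19. Showing an imbalance at Month 18 does not adjust for it. Nor is the model merely left open for the SAP: the protocol names both the booster model and its sensitivity model without the titer.

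**Conclusion.** The concern holds, as an improvement that should be made and not as an error that invalidates the analysis. No booster GMT model adjusts for the pre-booster titer. Under SD 0.51, a 54:27 split and equal pre- and post-booster SDs, this leaves the SE at 0.120 where adjustment would give 0.115, 0.105 or 0.086 at a correlation of 0.3, 0.5 or 0.7. If the correlation is low the gain is slight; if it is very high the fold-rise analysis captures nearly all of it. The benefit falls mainly on the size of the ratio and on Months 24 and 30.

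The main-phase point is minor. Stratified randomisation limits imbalance, and the omitted strata make the SE too large by a few percent at most under the assumed effects.

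**What to change.** **Booster.** Analyse log10 titer at Months 19, 24 and 30 by ANCOVA with treatment, site, age group and log10 pre-booster titer (Visit 8 or 9 sample) of the same serotype. Keep the planned ANOVA as sensitivity. Report how many subjects lack a pre-booster sample and so drop out of the adjusted model. Bring the fold-rise time points in section 9.3 into line with section 4.1 and the synopsis.

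**Timing.** Section 4.2.10 still puts the event in the future: "In the Booster Phase the study sponsor/collaboration partner and trial statisticians will be unblinded at the time of the Month 19 analysis". Specify the model before that snapshot. If it has already been taken, label the model as added later and supplementary. By the protocol's own estimates, Month 24 and Month 30 data were still being collected when version 6.0 was issued.

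**Main phase.** Add a model with treatment, site, age group and serostatus as main effects, without the interaction. It is supplementary for Day 208, which has already been analysed, and can be used for any main-phase time point not yet analysed.

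**Cost.** No new data: SAP text and one extra model per time point, with subjects lacking a pre-booster sample lost from the adjusted booster model.

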9.4 Safety Analysis

Main Study Phase:

All subjects entered into the study who received at least one vaccination (safety population) will be included in the safety analysis. Safety tabulations will generally be provided separately for solicited AEs and unsolicited AEs, and for both types of AEs combined. 95% confidence intervals according to Altman will generally be provided for all AE rates. Further details in addition to the outline below will be provided in the SAP.

The number and percentage of subjects with any AE, any unsolicited AE, any related unsolicited AE, any SAEs, any AESI, any related SAEs, any medically attended AE and any AE leading to withdrawal from further treatment, up to Day 208 and up to Day 545, will be presented for each treatment group, overall and by system organ class/preferred term. Differences between both dose (VLA15 135 µg w/ alum and VLA15 180 w/ alum) groups and the placebo group will be assessed for significance using Fisher's exact (Fisher-Freeman-Halton) test, whereby a significant overall test will be amended by pair-wise tests. In addition, the number and percentage of subjects with any AE, any unsolicited AE, any related unsolicited AE, any SAEs, any related SAEs, any AESI, any medically attended AE and any AE leading to withdrawal from further treatment will be presented grouped by onset within 28 days after the first, the second or the third vaccination.

The number and percentage of subjects with solicited local and systemic AEs within 7 days after each vaccination and within 7 days after any vaccination will be tabulated. Differences between treatment groups will be assessed for significance using Fisher's exact test, a significant overall test will be amended by pair-wise tests. The occurrence of solicited local and systemic AEs will also be tabulated by Subject Diary day.

Changes in laboratory values from study entry to end of treatment/follow-up will be analyzed descriptively and will be part of the unsolicited AE evaluation only in case of clinically relevant deviations. The frequencies of subjects with laboratory assessments outside the normal range, and with abnormal laboratory parameters falling into the grade 0 vs. 1 through 4 will be calculated. The frequency of subjects with urinalysis results according to the test manufacturer's results categories will be calculated.

It will be defined in the SAP which safety analyses will also be repeated stratified by baseline *B.b. s.l.* serostatus and by age.

Booster Phase:

All subjects included in the Booster Phase who received a booster vaccination will be included in the booster safety analysis (Booster Safety Population). The number and percentage of subjects with solicited local and systemic AEs up to 7 days after the booster vaccination, with any solicited or unsolicited AE, with any unsolicited AE, AESI, and SAE up to Visit 10 (Month 19) and with any AESI or SAE up to Visit 12 (Month 30) will be presented for each treatment group overall and by body system/preferred term. The safety analysis will be done in accordance to procedures used in the Main Study Phase.

9.5 General considerations for the determination of the optimal dose

Based on safety and immunogenicity results obtained from the Day 208 interim analysis of this study, the 180 µg dose was selected for further development. This is the highest dose investigated in the development program and is demonstrating a good safety profile and good immunogenicity. Sustained high levels of antibodies are of utmost importance for an OspA

based vaccine to confer protection. Hence, the 180 µg treatment group will be continued in further clinical development of this vaccine.

